4.3 Anticipated clinical Benefits

Reduction of IOP is to date the only proven therapy for glaucoma (Quigley, 2011). Improved control of IOP is linked to better long-term outcomes for glaucoma patients (King, 2013). Most of the currently available methods to measure IOP require office or clinic visits and are not feasible for frequent, round-the-clock or continuous use or for use in the patient's daily environment. At the same time, IOP fluctuates as a result of the patient's daily activities and circadian rhythm. Peak values – which are thought to be the most significant for long-term outcomes – are often not detected. Under normal clinical conditions for example in Germany, IOP of patients with diagnosed glaucoma is measured only once every 3 months, which does not provide enough information to adequately adjust patient treatment. The ARGOS-IO system makes numerous IOP measurements every day on a permanent basis, requiring only that the patient hold the external reader near the eye to activate the implant and download the readings several times daily. The physician is able to access the readings so recorded, thereby obtaining a complete profile of IOP changes, including peak values and values as influenced by all patient activities, for the entire time interval since the last treatment visit.

One objective of this study is to verify the device's accuracy in the patient population. Until this is done, only the control readings made via GAT will be used as the basis for treatment decisions. Study patients will however benefit from a more intensive than normal monitoring of their IOP during the study and are enabled to measure IOP daily themselves. If and when the device's usefulness has been verified, the patients and the general patient population will benefit from the increased insight gained from a continuous long-term monitoring of IOP independent from visits to the ophthalmologist. If the device proves successful, the Sponsor plans to develop an internet platform that will permit the physician to remotely access information from individual readings, allowing patients' IOP to be monitored between visits. This should permit a more rapid response to changes in IOP and a better fine-tuning of treatment protocols.

Because glaucoma progresses slowly and does not generally cause any immediate symptoms, patients have no way of registering the success or failure of their treatment between clinic visits. As a result, as with other chronic diseases, adherence to prescribed treatment regimens may be poor (Hermann, Bron, & Creuzot-Garcher, 2010). The consequences of poor IOP control are however serious and irreversible loss of vision and accompanying handicap. The frequent feedback the patient

IOP Implandata Ophthalmic Products GmbH	Clinical Investigation Plan ARGOS-03	Revision C Page 26 of 67
---------------------------------------------------	-------------------------------------------------------	-----------------------------

will receive from the device is expected to motivate better compliance with the treatment regimen, thereby facilitating improved IOP control and optimizing long-term patient outcome.

 Implantata Ophthalmic Products GmbH	Clinical Investigation Plan ARGOS-03	Revision C Page 27 of 67
--------------------------------------------------------------------------------------------------------------------------	-------------------------------------------------------	---------------------------------

5. STUDY OBJECTIVES

5.1 Objectives

The aim of this trial is to verify the long-term safety and performance of the ARGOS-IO system in patients with Primary Open Angle Glaucoma (POAG). The measurements of intraocular pressure through the pressure sensor shall be compared with Goldmann Applanation Tonometry (GAT), which is generally accepted as the clinical gold standard and the Pascal Dynamic Contour Tonometer (DCT).

5.1.1 Primary Objectives

5.1.1.1 Safety

- The primary objective of this clinical trial is to evaluate the long-term safety and tolerability of the ARGOS-IO pressure sensor under consideration of incidence, nature, severity and seriousness of observed medical device related adverse and serious adverse events.

5.1.1.2 Performance

- To evaluate the performance of the ARGOS-IO system compared to Goldmann Applanation Tonometry (GAT) and Pascal Dynamic Contour tonometry (DCT)
- Incidence and nature of observed device malfunctions of the ARGOS-IO system

5.1.2 Secondary Objectives

- Evaluating the patient's compliance in IOP self-monitoring
 - Daily self-measurements with the ARGOS-IO sensor should be done at least 4 times daily (morning, noon, afternoon, evening)
- Evaluating the impact of IOP self-monitoring on glaucoma progression
 - Parameters to evaluate the glaucoma progression are visual field, cup/disc ratio, OCT of the optic nerve and the IOP.
- Evaluation of incidence in glaucoma medication change
- Evaluation of number of unscheduled visits due to self-measured increased intraocular pressure
 - The patients decide to come for a visit by their own due to any reason. This will be documented.

 Implantata Ophthalmic Products GmbH	Clinical Investigation Plan ARGOS-03	Revision C Page 28 of 67
--------------------------------------------------------------------------------------------------------------------------	-------------------------------------------------	---------------------------------

5.2 Claims and intended Performance of the ARGOS-IO System to be verified

This study aims to estimate the agreement of measurements taken with the ARGOS-IO system to those obtained using GAT, Pascal DCT and to collect further information on the occurrence of ADEs and SADEs and about the reliability of the device in humans.

5.3 Risks and anticipated Adverse Device Effects to be assessed

Information will be collected on all ADEs. Particular attention will be paid to the following AEs (AEs of special interest):

- Signs of toxicity of the implant
- Uncontrolled increase in IOP
- Changes in anterior chamber structures including ACD and ACA
- Anterior chamber inflammation (Tyndall/flare/anterior chamber cells)
- Fibrin reaction (e.g. anterior chamber fibrin, fibrin deposition on lens)
- Corneal endothelial cell loss
- Pigment dispersion
- Iris transillumination defect

6. DESIGN OF THE CLINICAL OBSERVATIONAL STUDY

6.1 General Aspects

6.1.1 Description of the Type of Clinical Trial

The trial will be conducted as a prospective, open-label, multicenter clinical follow-up trial.

The trial will include the ARGOS-01 patients (max. 5 patients) and the ARGOS-02 patients (max. 21 patients). From the ARGOS-01 study to the ARGOS-02 study, some modifications to the form of the ARGOS-IO implant were made in consequence of the outcomes of the ARGOS-01 study.

The design modifications made included:

- Addition of 4 haptics at the outer edge of the implant
- Reduction in device thickness from a uniform 0.9 mm to 0.5 mm overall, tapering to a 0.1 mm rounded outer edge

 Implantdata Ophthalmic Products GmbH	Clinical Investigation Plan ARGOS-03	Revision C Page 29 of 67
---------------------------------------------------------------------------------------------------------------------------	-------------------------------------------------------	---------------------------------

- Addition of two allantoid protrusions running on either side of the posterior surface from the middle of the ring to the ASIC.

The ARGOS-IO implant used in the ARGOS-01 study had an outer diameter size of 11.3 mm, an inner diameter size of 7 mm and an overall thickness of 0.9 mm. In the ARGOS-02 study three different sizes were used: Ø 11.3 mm, Ø 11.7 mm and Ø 12.1 mm; all with an inner diameter of 7 mm and thickness of 0.5 mm.

All consenting ARGOS-IO patients are eligible for enrolment into the study.

6.1.2 Equipment to be used to assess the clinical trial variables and arrangements for monitoring maintenance and calibration

Sites will use their own ophthalmology diagnostic devices. The requested calibration intervals have to be followed.

Following any ocular procedure and at least once a year the correct function of the ARGOS-IO implant must be confirmed by an experienced and qualified specialist using GAT (the average of 3 ARGOS-IO measurements are compared to one GAT measurement), and adjusted if necessary (please refer to the *Mesograph IFU* for details).

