6.4.4 Assessments

6.4.4.1 *Patient Demographics/other Baseline Characteristics*

Patient demographic and baseline characteristic data to be collected on all subjects include: year of birth, sex, race, weight, height and educational level

6.4.4.2 *Comparative Measurements*

All ARGOS-IO measurements which were performed in the clinic between study end of the ARGOS-01/ARGOS-02 trial and which have a comparative GAT measurement should be entered in the eCRF.

6.4.4.3 *Medical History*

Relevant medical history/current medical condition data includes data five years back until start of the study and everything what is important of the investigator's point of view. Relevant medical history should be supplemented by review of the subject's medical chart and/or by documented dialog with the subject's referring physician. If possible, diagnoses and not symptoms are to be recorded.

6.4.4.4 *Concomitant Medication, Treatments and Devices*

There are no restrictions for the use of concomitant medications and treatments required for ophthalmological or systemic diseases during this clinical trial. The use of concomitant medication and treatments will be documented in the patient's file and in the CRF.

6.4.4.5 *ADEs/SAEs/SADEs*

All ADEs/SAE/SADEs will be recorded.

6.4.4.6 *Check of functionality of the Mesograph and Multiline Connector*

At V01, the Mesograph will be tested for no error messages, enough storage and filled charged battery. The Multiline Connector will be tested for proper data transmission. If necessary, the devices will be changed.

6.4.4.7 *Confirmation of the correct function of the ARGOS-IO sensor*

The correct function of the ARGOS-IO implant must be confirmed using GAT (the average of 3 EYEMATE-IO measurements are compared to one GAT measurement), and adjusted if necessary (please refer to the *Mesograph IFU* for details).

 Implantata Ophthalmic Products GmbH	Clinical Investigation Plan ARGOS-03	Revision C Page 34 of 67
--------------------------------------------------------------------------------------------------------------------------	-------------------------------------------------------	---------------------------------

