6.5 Study Visits

6.5.1 Baseline Visit, V01 (Day 0)

At the Baseline visit, the investigator will conduct the informed consent process (section 12.1), ensuring that the subject's signature has been obtained on the patient informed consent (PIC) form and that the subject has received a copy before any study specific procedures are conducted. Once the PIC is signed, the subject will be assigned a patient number (section 6.4.2).

In addition, the following procedures will be performed at this visit:

 Implantata Ophthalmic Products GmbH	Clinical Investigation Plan ARGOS-03	Revision C Page 38 of 67
--------------------------------------------------------------------------------------------------------------------------	-------------------------------------------------------	---------------------------------

- Collection of background information about the subject including: demographics, medical history with prior treatments and current medications and comparative measurements (see 6.4.4.2)
- Check of the functionality of the Mesograph and Multiline Connector (exchange if necessary)
- Confirmation of the correct function of the ARGOS-IO sensor (adjustment if necessary)
- Handout of patient diary
- Best corrected visual acuity (BCVA) using ETDRS
- Visual field (standard automated static perimetry, see section 6.4.4.8)
- National Eye Institute – Vision-related Quality of Life Questionnaire-25 (VFQ-25)
- Anterior Segment
 - External eye photography (Slit-lamp), including iris retro illumination
 - Slit-lamp biomicroscopy
 - OCT of cornea and anterior chamber
 - Corneal endothelial cell density measurement
 - Gonioscopy
- Posterior Segment Measurement
 - Funduscopy
 - OCT of macula and optic nerve
 - Fundus photography
- IOP Measurement:
 - GAT and ARGOS-IO system
 - 2x GAT, 3x ARGOS-IO (Measurement by investigator with the patient's head still in the headrest from GAT, see 6.4.4.12)
 - DCT and ARGOS-IO system
 - 2x DCT, 3x ARGOS-IO (Measurement by investigator with the patient's head still in the headrest from DCT, see 6.4.4.12)
 - ARGOS-IO self-measurements at home (4 measurements daily, "IOP-day" once a month see 6.4.4.12)
 - Instruct subjects on the need to report as soon as possible any SAEs occurring at any time during the study

 Implantata Ophthalmic Products GmbH	Clinical Investigation Plan ARGOS-03	Revision C Page 39 of 67

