7.1.4 Primary Outcome Variables

Safety:

- Incidence of medical-device related adverse events

 Implantata Ophthalmic Products GmbH	Clinical Investigation Plan ARGOS-03	Revision C Page 43 of 67
--------------------------------------------------------------------------------------------------------------------------	-------------------------------------------------------	---------------------------------

- Incidence of medical-device related serious adverse event.
 - o An AE is considered to be device-related if there is at least a possible relationship to the medical device according to the rating of the investigator
 - o An AE is considered to be serious if it meets any of the criteria defined in Section 9.1.1.2

The analysis will be split by nature, severity and seriousness of medical device related adverse and serious adverse events.

Performance:

- Limits of agreement between IOP measurements made using GAT and the ARGOS-IO system at each study visit.
- Limits of agreement between IOP measurements made using DCT and the ARGOS-IO system at each study visit.
- Incidence of observed device malfunctions and nature of device malfunction (e.g. difference of more than 5 mmHg between ARGOS-IO and GAT, readout error of the Mesograph because of measurements outside -2 and +70mmHG).

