7.8 Datasets to be analyzed

All subjects enrolled in this study will be included in the analysis since all subjects already have the ARGOS-IO sensor implanted and evaluable data for the primary performance are already recorded at the baseline visit (V01). As described in the previous section, the handling of missing data will be detailed in the statistical analysis plan. Depending on the number of drop-outs during the course of the study, sensitivity analyses with subsets of subjects might be planned in the SAP if deemed necessary for the correct interpretation of the results.

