## 7.5 Evaluation of Primary Performance Variables

### Limits of agreement

The Bland-Altman method, which compares the mean of paired measurements to their difference, will be used to determine the upper and lower limits of agreement expected to contain 95% of the IOP value pairs obtained with the ARGOS-IO system and GAT. The agreement evaluation will follow

the publication of Zou (2011)b. Zou describes two cases, namely Case I for the assumption that the true value varies over time and Case II for the assumption that the true value is constant over time. Case I requires a pairing of measurements between devices while Case II requires no pairing. Since within each visit only one series of GAT measurements is done and GAT measurements are done consecutively followed directly by the measurements with the ARGOS-IO system, no pairing is possible, and Case II is assumed for the evaluation for data within a visit. By assumption of Case II, it is not necessary to calculate the mean of each series with the respective device, but data can be used as available for the analysis per visit. Please note that this procedure differs from the CIP since it was originally assumed that several series of measurements per visit would be available. The two-sided 95% confidence intervals for each of the agreement limits will be calculated using the Mover method to account for repeated observations. In case of the overall analysis, available data of all visits are included under assumption of Case I since it can not be assumed that the IOP is constant between visits. For this purpose, the mean of each measurement series will be calculated and used for evaluation of limits of agreement as described in the CIP. IOP values will be displayed as Bland-Altman plots of individual measurement pairs by measurement technique for each visit and overall. The limits of agreement between the ARGOS-IO system and DTC measurements will be also calculated by the described procedure.

The difference of measurements between the ARGOS-IO measurements and GAT / DTC will further be summarized per visit using descriptive statistics. The difference per subject will be calculated as the difference between mean of ARGOS-IO values and mean of GAT / DTC values of the same series (Difference = mean of ARGOS-IO values – mean of GAT/DTC values).

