## 7.6 Evaluation of Secondary Variables

### Progression analysis

Summary statistics for raw values and change over time will be provided for visual field, cup/disc ratio and IOP (for all types of measurements) by eye and visit. Frequency tabulations (absolute and relative) will be prepared for OCT results for the optic nerve over the course of the study, by eye and visit. The denominator for the calculation of relative frequencies will be the number of subjects attending the respective visit.

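### ARGOS-IO may be adjusted after a check against GAT, its own comparator, and the plan does not order the check against the comparison series, require adjustments to be recorded, or separate the readings that follow

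*Protocol*

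**What the plan says.** Protocol 6.1.2 requires the implant's function to be confirmed after any ocular procedure and at least yearly: "the average of 3 ARGOS-IO measurements are compared to one GAT measurement), and adjusted if necessary". It refers to the Mesograph instruction for use (IFU) for details. Section 6.4.4.7 repeats the rule under another product name: "the average of 3 EYEMATE-IO measurements are compared to one GAT measurement), and adjusted if necessary". The V01 procedure list in 6.5.1 includes "Confirmation of the correct function of the ARGOS-IO sensor (adjustment if necessary"). Table 1 of the protocol and Table 1 of the SAP mark this check at V01 only.

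GAT is also the comparator for the first primary performance variable in protocol 7.1.4: "Limits of agreement between IOP measurements made using GAT and the ARGOS-IO system at each study visit". Section 7.8 treats V01 as part of this, because "evaluable data for the primary performance are already recorded at the baseline visit (V01").

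SAP 7.5 uses all available readings for the limits at each visit and then pools: "In case of the overall analysis, available data of all visits are included under assumption of Case I". It also summarises, per subject and visit, "the difference between mean of ARGOS-IO values and mean of GAT / DTC values of the same series". SAP 7.6 reports raw values and change over time for "visual field, cup/disc ratio and IOP (for all types of measurements) by eye and visit".

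**The concern.** The device under test can be adjusted, during the study, by reference to the method it is being compared with. That would be manageable if the comparison were always taken first, or if adjustments were logged and used in the analysis. The plan provides for neither.

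Long-term performance is the stated aim. Protocol 4.2 reports pressure drift in ARGOS-01, whose patients are eligible here. Protocol 7.2.4 expects a real systematic shift between ARGOS-IO and indirect tonometry. An offset towards GAT could reduce both the drift and the shift in the reported results. Three results would be touched:

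- the GAT mean difference and its course over visits;
- DCT agreement, because the same ARGOS-IO offset enters that comparison;
- the ARGOS-IO change from V01 in SAP 7.6, where an adjustment made after the V01 series would read as a change in IOP. The GAT and DCT changes are unaffected.

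**Working it through.** **Reading the documents**

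1. *Order.* Protocol 6.4.4.15 and the IOP footnote to Table 1 order the GAT, DCT and ARGOS-IO readings within a series. They do not place the check. The V01 list in 6.5.1 names the check above the IOP series, which suggests that it comes first, but no sentence makes the list a sequence. The yearly and post-procedure checks have no place in either schedule.
2. *Recording.* Protocol 6.4.4.8 and 9.1.4 require malfunctions and deficiencies to be recorded, and section 8 requires relevant study data to be captured. None of them names an adjustment, its date or its size. SAP section 6 and the SAP appendix contain no such variable, table or listing.
3. *Analysis.* SAP 4.2 (subgroups), 5.1 (missing data and outliers), 7.5, 7.6, 7.9 (special issues) and 8 (changes) do not mention adjustment.
4. *Malfunctions.* Protocol 7.1.4 gives an ARGOS-IO/GAT difference above 5 mmHg as an example of a malfunction. SAP 7.5 counts only malfunctions that a medical expert picks from filed deficiencies, although the same section already computes the per-subject difference from which this example could be derived.
5. *Schedule.* The check is at least yearly in 6.1.2 but at V01 only in Table 1. A smaller mismatch: 6.4.3.2 records deficiencies at each visit, whereas Table 1 starts at V02. The general duty to record still covers V01.

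**Illustrative arithmetic**

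Inputs, from protocol 4.2: ARGOS-02 mean difference 2.8 mmHg with limits -1.7 to 7.4; ARGOS-01 mean difference 10.2 mmHg. Differences are assumed normal.

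- *The plan's own figure.* SD = (7.4 + 1.7) / (2 × 1.96) = 2.32. Then 2.8 ± 1.96 × 2.32 = -1.75 to 7.35, which matches the stated limits to rounding.
- *Share beyond 5 mmHg, no adjustment.* P(|D| > 5) with mean 2.8 and SD 2.32 = 0.172.
- *Common shift to zero, SD unchanged.* Limits 0 ± 1.96 × 2.32 = ±4.55; P(|D| > 5) = 0.031.
- *Eye-by-eye reset of every eye.* Let p be the share of variance that persists within an eye, and let check and series have independent errors of equal variance. This is a simplification, because the check uses one GAT reading and the series at least two. After the reset, only series error minus check error remains, so SD = 2.32 × √(2(1 − p)).

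| p | SD | limits |
|---|---|---|
| 0.3 | 2.75 | ±5.38 |
| 0.5 | 2.32 | ±4.55 |
| 0.7 | 1.80 | ±3.52 |

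Against ±4.55 around the unadjusted mean, the limits widen when p is below 0.5 and narrow when it is above.

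- *ARGOS-01 eyes.* If the earlier mean differences persisted and all 26 patients enrolled, the unadjusted mean would be (5 × 10.2 + 21 × 2.8) / 26 = 109.8 / 26 = 4.2 mmHg. The 2.8 mmHg of ARGOS-02 is therefore not an upper bound on the shift in this cohort.

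**The case against.** The trigger, the direction and the meaning of an adjustment are delegated to the IFU, and logging may be specified in the eCRF or the data management plan. None of these was supplied. That stands: the direction towards GAT is an inference, and the statement about recording is limited to the protocol and SAP. It does not close the gap, because the SAP makes no use of such a log even if one exists.

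A sensor found to be off at the check might also be filed as a deficiency, and the SAP lists deficiencies. That would capture some triggers, but nothing requires the size of the correction to be stated.

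A reader might infer that adjustment hides drift altogether. The documents do not support that. SAP 7.5 gives difference summaries and Bland-Altman plots per visit, and the appendix lists IOP by visit. A step could show there, although its cause would not be identified. Drift between checks stays visible, and if the check is done only at V01, before the series, so does all drift after it.

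A reader might also infer that adjustment must narrow the limits. The working shows that they can move either way.

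Finally, the study is exploratory, with no hypothesis and no acceptance limit, and agreement of the system as maintained is a legitimate target. Both points are fair. But estimates are then the whole product, and a reader needs to know whether an estimate describes a stable sensor or a re-centred one.

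**Conclusion.** The point holds and should be fixed. Followed as written, the plan can adjust ARGOS-IO by reference to GAT and then use those readings in the per-visit and pooled agreement with GAT, with no stated order, no required record and no flag.

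If the adjustment is an offset towards GAT, the GAT mean difference is expected to move towards zero. DCT agreement would shift by the same offset, and the ARGOS-IO change from V01 would be affected by any adjustment made after the V01 series.

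The size cannot be determined, because no rule, rate or amount of adjustment is given. The change from about -1.7 to 7.4 to about ±4.55 mmHg, and from 17% to 3% beyond 5 mmHg, illustrates a common shift only. It rests on normality and on ARGOS-02 values whose own adjustment history is not stated. It is not a forecast: ARGOS-01 eyes could shift more.

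It would go too far to conclude that the agreement results are circular or invalid. The documents do not say how often, by how much, or at what point in a visit any adjustment is made.

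**What to change.** - **Visits still to come:** take the GAT/ARGOS-IO and DCT/ARGOS-IO series before any adjustment at that visit. Record the date, size and reason of each adjustment if this is not already captured.
- **SAP 7.5 and 7.6:** list adjustments, and flag post-adjustment readings both in the agreement analysis and in the ARGOS-IO change from V01. Add a supplementary limits-of-agreement analysis by adjustment status where the SAP 4.2 minimum is met (at least two groups with five or more patients); otherwise give a listing. Keep it descriptive, because adjustment status is likely to depend on the size of the difference. Leave the primary analysis unchanged.
- **Malfunctions:** report a programmed count of ARGOS-IO/GAT differences above 5 mmHg, from the visit means and including V01, beside the expert-identified malfunctions.
- **Where no adjustment records exist:** state that agreement and drift are those of the system as maintained.
- **Consistency:** reconcile 6.1.2 with Table 1 on when the check is done and, as a minor item, 6.4.3.2 with Table 1 on deficiency recording.

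The cost is a few eCRF fields if they are missing, SAP wording and some programming. The SAP was finalised in May 2022, so reordering may be too late for completed visits. The programmed count and the limitation statement remain possible, as do the flags where records exist. Agreement may look less favourable.
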